## 7.6 VISIT WINDOWING

Assessments that do not have cycle and day/visit allocated or pre-specified in the datasets will be assigned to cycles based on the collection date of the sample relative to the start dates of the cycles from the study drug administration page.

## 7.7 CENTRAL REVIEW AND ASSESSMENT

Central review will be done in a blinded and independent manner by two image evaluators (readers). Where there is non-agreement between the two response evaluations, a third party adjudicator will indicate which evaluation will be considered in the analysis.

## 7.8 LABORATORY DATA CONVERSIONS

### 7.8.1 GENERAL

All laboratory data will be displayed as recorded on the eCRF. Laboratory values collected as a range may be converted to numeric values when evaluating abnormalities, but should not be included in calculations of change from baseline.

Data collected as inequalities (e.g.,  $>5$ ,  $<5$ ,  $\geq 5$ ) will be converted to numeric values for evaluating abnormalities but will not be included in summarizations or descriptive displays such as change from baseline. Data using the form of " $>5$ " or " $<5$ " are converted to numeric by adding or subtracting a "fuzz factor" 0.001 (e.g.,  $<5$  should be

4.999 and >5 should be 5.001). Data using the form “<=” or “>=” will be converted to the numeric value (e.g., <=5 should be 5). Reference ranges that are recorded as a less than value (e.g., <10) should be placed in the database as a zero to that value (e.g., 0 – 10).

### 7.8.2 CONVERTING RANGE DATA TO NUMERIC

1. Determine that the LABVALUE is composed of two numeric words separated by a hyphen or blanks and a hyphen.
2. Establish the range as the highest and lowest values.
3. Test that the first value in the range is less than or equal to the second. If not, output an error message and set the numeric output variable to a SAS missing value.
4. The numbers resulting from a textual conversion, the reference limits, and the lower and upper abnormality limits are rounded using a “fuzz factor.” This eliminates digits that could cause two values to compare unequally due to rounding errors made by the computer.
5. If both lower and upper range values are within the normal limits, then assign the midpoint of the lower and upper range values to the numeric lab test result variable.
6. If the lower range value is below the lower limit of normal, but the upper range value is within the normal limits, then assign the lower range value to the numeric lab test result variable.
7. If the upper range value is above the upper limit of normal, but the lower range value is within the normal limits, then assign the upper range value to the numeric lab test result variable.
8. If the lower range value is below the lower limit of normal and the upper range value is above the upper limit of normal then an error condition exist. The range in the text lab value should not span the normal limits.

### 7.8.3 DIFFERENTIALS

Hematology results include neutrophils, lymphocytes and eosinophils recorded as absolute cell counts and/or percent of the white blood cell counts. For summarization purposes, percent values may be converted to absolutes by multiplying the percent value by the white blood cell count at the same time point. Listings will display the original values.

## 7.9 EXAMINATION OF SUBGROUPS

Subgroup analysis will be described in section 9 of the SAP.

## 7.10 STATISTICAL COMPARISON METHODS

No comparisons will be made.

## 7.11 STATISTICAL SIGNIFICANCE

Not applicable

## 7.12 MISSING DATA

### 7.12.1 IMPUTATION OF NON-DATE MISSING DATA FOR STATISTICAL ANALYSES

Unless otherwise explicitly specified, missing data will not be imputed. All available time to progression or death data will be analysed using appropriate statistical methods that allow for censoring when no progression or death is reported. Subjects with reported shorter treatment and/or follow-up intervals will not be considered to have missing time to progression or death status. Subjects with premature study withdrawal (including lost to follow-up) will be included in any analyses where they contribute data and where they conform to the analysis population of interest.

Subjects without baseline tumor assessments will be considered non-evaluable for ORR and irORR analysis.

When using RECIST v1.1 or irRC criteria to estimate the proportion of responders, all subjects in Response Evaluable Set will be included in the denominator even when their responses are missing.

### 7.12.2 HANDLING OF MISSING AND NON-QUANTIFIABLE DATA FOR PHARMACOKINETIC ANALYSES

Concentration data will be considered missing if:

- No sample is collected
- A sample is collected but no valid bioanalytical data are reported for any reason

Missing values will be considered missing for the purposes of listing, summarization and analysis, with the exception that Cycle 1 Day 1 pre-dose concentrations will be set to “0” if missing for the purposes of NCA analysis.

If a sample is collected and analysed, but is of questionable identity due to possible sample handling or labelling errors either at the clinical site or the bioanalytical lab, the concentration will be reported and flagged in the listings, and the rationale for considering the identity questionable will be documented. The data will be set as missing in the primary NCA analysis and statistical summarization, but a sensitivity analysis may be conducted in which the concentration data point is included in the NCA and statistical summarization for NCA results for the relevant Dose and Cycle repeated.

If a quantifiable concentration is available but the actual sampling time is missing, the nominal sampling time will be used.

Bioanalytical data that are below the limit of quantitation (BLQ) will be treated as follows:

- For listings, BLQ will be reported as “< LLQ” (lower limit of quantitation)
- For NCA, BLQ concentrations will be set to 0

## **8. ENDPOINT DEFINITIONS AND DERIVATIONS**

### **8.1 SAFETY DEFINITIONS AND ENDPOINTS**

#### **8.1.1 ADVERSE EVENT ENDPOINTS**

Adverse events will be categorized by pre-existing, treatment emergent and post treatment.

- Pre-existing AEs are designated to events that occur prior to the first dose of study drug(s) or observed prior to first dose but did not increase in NCI CTCAE toxicity grade during treatment period.
- Post-treatment adverse events will be any adverse events reported outside the 28 day post dose treatment window until the end of study participation. Any subsequent non-protocol treatment for the cancer diagnosis will end the potential study drug(s) adverse event data collection.
- Treatment-Emergent Adverse Events (TEAEs) are designated to events that occur after the start of study drug(s) and on or before 28 days after final dose of study drug, and were not observed prior to start of treatment; Or if the event was observed prior to the start of study drug but increased in NCI CTCAE grade after either the start of study drug or prior to 28 days after the final dose of study drug. Pre-existing adverse events may be reclassified as TEAEs if the frequency of the event increases during treatment.
- Treatment Related TEAEs will include those TEAEs which are possibly or probably related to study drug(s) as designated by the investigator. Events having a missing relatedness will be designated as definitely related on tables but the listing will display the data as collected. Relationship may be attributed by JTX-2011 and/or nivolumab/ipilimumab/pembrolizumab and will be displayed separately.
- Serious adverse events (SAEs) will include all events classified as serious on the eCRF. The electronic database used to enter data at the site (i.e., RAVE / iMedidata) will be deemed as the complete report for adverse event information. The pharmacovigilance database will be reconciled against the EDC.

- Infusion related reactions (IRRs) may be captured as an adverse event as well as the symptoms that cause the IRR. Symptoms of IRRs are events occurring shortly after or during the study drug infusion. Symptoms may include but are not limited to: flushing, headache, nausea, fever, chills, dyspnea, rash, hypotension, wheezing, coughing, tachycardia. Any sign/symptom determined to be associated with an IRR may be counted as such in adverse event reporting. The highest grade sign/symptom must be associated with the IRR preferred term.
- Immune-related adverse reactions (irAEs) are unique side effects typically seen after dosing with checkpoint inhibitors. At a minimum, the following have been associated with irAEs and will be evaluated for incidence in the combination arms: pneumonitis, colitis, hepatitis, endocrinopathies (hypophysitis), adrenal insufficiency, hypothyroidism and hyperthyroidism, type I diabetes mellitus, nephritis (defined as renal dysfunction or  $\geq G2$  increased creatinine requiring corticosteroids), rash, encephalitis (neurologic signs/symptoms), others include: motor dysfunction, vasculitis, myasthenic syndrome. Some ipilimumab associated irAEs include but are not limited to: uveitis, iritis, pancreatitis, facial and abducens nerve paresis, demyelination, polymyalgia rheumatica, autoimmune neuropathy, Guillain-Barre syndrome, hypopituitarism, system inflammatory response syndrome, gastritis, duodenitis, and sarcoidosis.

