9.4.8.1. Adverse Events

Adverse events will be classified into standardized terminology from the verbatim description (Investigator term) according to the most recent version of the MedDRA adverse event coding dictionary at time of data analysis. Adverse events will be presented by Preferred Term nested within System Organ Class (SOC). Verbatim description and Preferred Term and SOC MedDRA-level terms for all AEs will be contained in the data listings of the Clinical Study Report for this protocol.

Adverse events will be summarized by the incidence of AEs/SAEs by body system and by preferred term. The incidence of AEs/SAEs will be based on the numbers and percentages of subjects with AEs/SAEs. Although a MedDRA term may be reported more than once for a patient, that patient will be counted only once in the incidence count for that MedDRA term. The severity of the AEs/SAEs and the relationship to the study drug will be summarized for each body system and preferred term by treatment group. Withdrawals due to AEs/SAEs will be summarized for each body system and preferred term.

AEs/SAEs will be classified based on the AE start date in relation to the first dose date as the following:

- Treatment-emergent AEs, defined as AEs that newly emerge, re-emerge or worsen on or after the first dose of study drug; all these AEs would have a start date on or after the first dose date of the study drug.
- Pre-treatment events, defined as AEs that newly emerge, re-emerge or worsen before the first dose of study drug; all these AEs would have a start date before the first dose date of the study drug.
- Post-treatment events, defined as AEs that newly emerge, re-emerge or worsen after the treatment emergent period (defined in SAP) of the study drug; all these AEs would have a start date after the last day of the safety window of the study drug.

Only treatment emergent AEs will be summarized. All adverse events will be included in all AE data listings with flags indicating treatment emergent, pre- or post-treatment.

In consideration of the varying durations of treatments, the incidence of treatment emergent adverse event will be presented in the following ways, as appropriate, (1) by cohort and overall; (2) by time interval, depending on the distribution of duration of treatment, e.g., by 1-, 3-, 6-, or 12-month intervals from start of therapy; and (3) by event rate per patient year (i.e., # of events per patient per year).

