### 9.9.1 ADVERSE EVENTS

Adverse events (AEs) will be listed and summarized using MedDRA v19 coded terms. Listings will be created by categories for AEs as outlined below:

- All adverse events (AEs) with flags for treatment emergent adverse events (TEAEs) and flags of relatedness to study drug(s)
- SAEs with flags for treatment emergent adverse events (TEAEs) and flags of relatedness to study drug(s)
- Immune related adverse events (irAEs)
- Infusion related reactions (IRRs)
- TEAEs leading to death
- TEAEs leading to study drug interruption, reduction, hold or permanent study drug discontinuation
- TEAEs considered as DLTs

A general overview summary table will include frequencies by category of AE (as listed above) and will also include TEAE by severity grade and relationship to study drug (both JTX-2011 and/or nivolumab and/or ipilimumab and/or pembrolizumab).

Frequencies and percentages will be reported by System Organ Class (SOC) and Preferred Term (PT). Patients with multiple events for a category will be counted once in the highest CTCAE classification. Summary tables will include treatment-emergent AEs, unless specified otherwise. Missing onset date for an event will be considered as TEAE. If relatedness is missing the adverse event will be considered related. The denominator (N) for adverse events reported at each cycle will include SAF patients who are dosed at least once in that cycle. Important note: Patients will be counted in terms of number and adverse event in the actual dose group as received, not the as intended dose group. Summary tables by SOC and PT will be sorted in descending frequency of SOC for the total column, then in descending frequency of PT within SOC for the total column. Summary tables by PT will be sorted in descending frequency of PT for the total column.

The following summary TEAE tables listed in Table 7 below will be presented for Phase 1 and Phase 2 parts. In addition, DLTs will be summarized by SOC and PT only for Phase 1 parts (A, B, E, G) for DLT Evaluable Set.

Table 7 Summary of Adverse Event Displays

Category	TEAE	IRR	irAE	TEAE Related to JTX2011	TEAE Related to Any Study Drug	Serious TEAE	Related SAE	TEAE Resulting in Death	TEAE Resulting in Dose Interruption, Reduction or Hold	TEAE Resulting in Study Drug Discontinuation
SOC and PT	X			X	X	X	X			
SOC/PT/Max. Grade	X			X	X					
SOC/PT/Max. Grade $\geq 3$				X						
SOC/PT by Cycle	X									
SOC/PT by Grade, Cycle										

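### SAP 8.1.1 omits the protocol's re-emergence criterion, so by default an adverse event that resolved before first dose and returned at the same or a lower grade is not treatment-emergent

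*SAP*

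**What the plan says.** **Protocol 9.4.8.1** gives three ways to qualify: "Treatment-emergent AEs, defined as AEs that newly emerge, re-emerge or worsen on or after the first dose of study drug". Onset date governs: "all these AEs would have a start date on or after the first dose date of the study drug". On what is tabulated it says "Only treatment emergent AEs will be summarized"; the other events appear in listings with flags. The section leaves the length of the treatment-emergent period to the SAP. It does not leave the criterion for emergence to it.

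**SAP 8.1.1** gives two ways. An event qualifies if it falls between the start of study drug and 28 days after the final dose "and were not observed prior to start of treatment". The alternative is "Or if the event was observed prior to the start of study drug but increased in NCI CTCAE grade". Pre-existing events are those that occur before first dose, and also those "observed prior to first dose but did not increase in NCI CTCAE toxicity grade during treatment period". One further sentence softens this: "Pre-existing adverse events may be reclassified as TEAEs if the frequency of the event increases during treatment".

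**SAP 9.9.1** then states: "Summary tables will include treatment-emergent AEs, unless specified otherwise". All adverse events and all serious adverse events are listed, with a treatment-emergent flag.

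**Protocol 8.14.2** sets what can be on record before dosing. Collection starts at the main consent, with onset and resolution dates. Events after the pre-screening consent alone are not collected.

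**The concern.** The SAP is meant to carry out the protocol's definition, but it narrows it and gives no reason. An event that settled before dosing and then came back on study drug has a new onset date after first dose. That is the pattern the protocol's wording on returning events captures. Under the SAP's text the earlier episode disqualifies the later one unless the later one is of higher grade.

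Safety and tolerability are primary objectives in every part that the SAP analyses, and treatment-emergent incidence and severity is one of the listed safety endpoints (protocol 9.1.1). The omission works in one direction: it can remove events from the treatment-emergent tables and cannot add any. Because the frequency sentence is discretionary, two programmers following the same SAP could also produce different tables.

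**Working it through.** The plan states no figure on this point, so the check compares the two definitions case by case.

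Take an event recorded after consent, with any treatment-phase episode inside the 28-day post-dose window.

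| Case | Protocol 9.4.8.1 | SAP 8.1.1 |
|---|---|---|
| (a) Resolved before first dose; returns at same or lower grade; frequency not increased | Treatment-emergent | Pre-existing |
| (b) As (a), but frequency increased | Treatment-emergent | Pre-existing by default; may be reclassified |
| (c) Resolved before first dose; returns at a higher grade | Treatment-emergent | Treatment-emergent |
| (d) Ongoing at first dose, unchanged | Pre-treatment | Pre-existing |
| (e) Started and ended before first dose; never returns | Pre-treatment | Pre-existing |

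The documents agree in (c), (d) and (e). They conflict in (a), and the outcome in (b) is undetermined.

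**A concrete record for (a).** A subject has Grade 2 diarrhea in screening, which resolves, and Grade 2 diarrhea with a new onset date on Day 30. Under the protocol the event returned after first dose, so it is treatment-emergent. Under the SAP it had been seen before treatment, so the first route fails. Its grade is no higher, so the second route fails. It fits the description of a pre-existing event. One episode before dosing and one after need not be an increase in frequency.

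**Consequence.** By SAP 9.9.1 the record leaves the treatment-emergent summaries and the subsets built on them, such as related and serious treatment-emergent events. It stays in the listings.

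**Size.** For one preferred term in one cohort,

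loss in incidence = k / N,

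where N is the number treated and k is the number of subjects whose only on-treatment episodes of that term are of type (a), or type (b) left unreclassified. Subjects are counted once per term, so anyone with another qualifying episode of the term does not contribute to k. The documents give no adverse event counts, so k is unknown. With the planned cohort size of about 15, each such subject costs 1/15 = 6.7 percentage points for that term. This is the effect per subject and not an estimate of the loss. The earlier episode must both begin and resolve between main consent and first dose, and screening lasts up to 28 days (protocol 7.1), so k is probably small.

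**The case against.** **The reference grade is not stated.** SAP 7.3 sets the default baseline as the last value before first dose. If that governed adverse event grades, a resolved event would stand at zero and any recurrence would be an increase. Similarly, if each episode were a separate event, a recurrence would not have been seen before. SAP 9.9.1 counts an event with missing onset as treatment-emergent, which fits an onset-based view. These readings are possible, but 8.1.1 states neither. The frequency sentence also points the other way: it presupposes that a returning event remains pre-existing unless someone reclassifies it. The ambiguity is therefore a further reason to fix the text. It does not remove the conflict.

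**The frequency sentence already lets recurrences back in.** It lets in some, at discretion and on an undefined measure. It does not restore the protocol's rule.

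**Nothing is hidden.** This is correct as far as the listings go. In addition, the columns of SAP Table 7 for infusion reactions, immune-related events and related serious events are not labelled treatment-emergent, although the table is introduced as a set of treatment-emergent summaries. Complete loss from every table is therefore not established. The dose-limiting toxicity definition (protocol 6.3) does not use treatment-emergent status, so it is unaffected.

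**Earlier immunotherapy toxicity.** A reader might infer that a rash on a previous PD-1 inhibitor also counts as seen before, and hence that D01, D02 and D04, which require prior PD-1 therapy, lose most. The SAP does not say this. Section 8.1.1 categorises adverse events, which are collected from consent, while medical history is taken and summarised separately (protocol 8.2, SAP 9.3). This objection stands and limits the point to events arising after consent.

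**Conclusion.** The conflict holds on the plain text. SAP 8.1.1 drops re-emergence, and a same-or-lower-grade recurrence of an event that resolved before first dose is pre-existing by default. The bias can only be downward. Its size cannot be computed from the documents and is probably small.

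This rests on two assumptions: that the earlier grade is the reference for an increase, and that the same event term before and after dosing is one event. Both are the natural reading of 8.1.1, though neither is spelled out.

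Two stronger conclusions are tempting but not supported. One is a percentage loss of treatment-emergent events, which would need counts of earlier episodes and recurrences that the documents do not contain. The other is that the primary safety endpoint is compromised. Protocol 9.1.1 lists seven safety endpoints without ranking them, and treatment-emergent incidence is one of them.

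**What to change.** In SAP 8.1.1:

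- Add a third route to the treatment-emergent definition: *or an event that had resolved before first dose and re-emerges, at any grade, with a start date on or after first dose and within 28 days after the final dose*.
- Keep episodes that started and ended before first dose as pre-existing, which matches the protocol's pre-treatment category. Limiting pre-existing to events ongoing at first dose would leave a screening event that resolved and never returned without a category.
- Class events ongoing at first dose as pre-existing unless they worsen from their grade at first dose. This settles the reference grade.
- Turn the frequency sentence into a fixed rule with a defined measure, or delete it.

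If the narrower definition is intended, the SAP should say so and give the reason, and the clinical study report should record the departure, as protocol 9.5.2 requires for changes in method.

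The onset and resolution dates needed are already collected. The cost is slightly higher treatment-emergent rates and a fresh round of SAP signatures, which SAP section 2 requires for any update after approval.

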5.5. Part C (JTX-2011 Monotherapy Phase 2)

Part C will include approximately 15 subjects in each of 8 dose cohorts (total of 120 subjects) in the indications listed below at 0.3 mg/kg in both the q3w and q6w dosing schedule. All subjects must have progressed on or after all approved therapies. If prior therapy included a PD-1 inhibitor, subjects must have progressed after at least 2 months of this therapy:

q3w JTX-2011 dosing

- C01: HNSCC;
- C02: NSCLC;
- C03: Any tumor type other than those eligible for C01, C02, C04, or C05 (*closed to enrollment*);
- C04: Gastric cancer or gastroesophageal junction adenocarcinoma;
- C05: MSI-H or dMMR endometrial cancer (*closed to enrollment*);

- C06: TNBC that is immunotherapy naïve;
- C07: Mesothelioma that is immunotherapy naïve.

q6w JTX-2011 dosing

- C64: Gastric cancer or gastroesophageal junction adenocarcinoma

Pre-screening for ICOS will not be required. Subjects in Part C are required to have archival tumor and two fresh tumor biopsies (one during screening and one post-dose between C2D1 and C3D1 for subjects on the q3w, or between C2D1 and C2D22 for subjects on the q6w). In situations where archival tissue is not available or biopsies are not feasible (e.g., would expose the subject to unreasonable health risks), one or more of these requirements may be waived after discussion with the Medical Monitor.

To complete enrollment in the HNSCC (C01), NSCLC (C02), gastric (C04 and C64), and TNBC (C06), at least 15 assessable pre-treatment fresh biopsies must have been obtained in each cohort, 10 of which must have an ICOS score ≥ 2 . To complete enrollment in the mesothelioma cohort (C07), 10 subjects must have enrolled with ICOS ≥ 2 based on archival tissue, rather than fresh tissue.

If a subject has progressed in Part C, nivolumab can be added to the subject’s treatment regimen after confirmation of progression and at the discretion of the Sponsor and investigator. After the completion of Part G, instead of nivolumab, pembrolizumab can be added to the subject’s treatment regimen upon confirmation of progression and at the discretion of the Sponsor and investigator. Confirmatory scans may be performed no less than 4 weeks from the most recent radiographic assessment documenting disease progression.

Figure 6: Part C q3w Treatment Schema

[figure not shown]
[figure not shown]

Figure 7: Part C q6w Treatment Schema

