6.7. Criteria for Dose Modifications

6.7.1. Delayed Cycles

A change in the start of a cycle of +3 days for social reasons (e.g., holidays) is permitted if unavoidable. Subjects who require frequent treatment delays should be discussed with the Medical Monitor.

Subjects requiring a delay of a scheduled cycle starting on or after Cycle 3 due to treatment-related toxicities that have not resolved are to be managed as follows:

- If the delay is ≤ 7 days, treatment should resume at the assigned dose level.
- If the delay is > 7 days but ≤ 14 days, treatment should resume at the next lower dose level.
- If the delay is more than 14 days, further course of treatment should be discussed with the Medical Monitor.

If a cycle delay of > 14 days not due to treatment-related toxicity occurs, the circumstances surrounding the delay will be discussed with the Medical Monitor prior to dosing the patient for the next cycle.

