7.2.11. Response Assessments

With the exception of prostate cancer subjects in Parts E and F, post-baseline response assessments in this trial are to be performed every 9 weeks (-10 days).

- For q3w subjects: Response assessments will be performed within 10 days of C4D1, C7D1, C10D1, and every three cycles thereafter.
- For q6w subjects: Response assessments will be performed approximately every 1.5 cycles, i.e., mid-Cycle 2, end of Cycle 3, mid-Cycle 5, end of Cycle 6, etc.

For prostate cancer subjects in E and F, post-baseline response assessments and a bone scan will be performed every 12 weeks (-10 days), i.e., within 10 days of C3D1, C5D1, C7D1, and every two cycles thereafter.

The imaging interval may be increased to every 12 weeks with a +/- 3 week window for subjects who remain on study treatment for ≥ 24 months

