7.3. Assessments for Subjects in Part C After Adding Post-Progression Nivolumab

7.3.1. Cycle X Day 1

The following evaluations and procedures will be performed during this visit (± 3 days):

- Physical examination.
- Vital signs pre-and post-infusion.
- Weight.
- ECOG performance status.
- Pregnancy test for WOCBP.
- 12-lead ECG.
- Laboratory assessments: Chemistry, hematology, coagulation, thyroid function, and urinalysis. Laboratory assessments need not be repeated if they were performed within 72 hours of the Day 1 visit.
- Blood samples for PK.
- Record concomitant medications.
- Adverse events assessment.
- JTX-2011 Administration followed by observation for at least 1 hour.
- Nivolumab or pembrolizumab administration followed by observation for at least 1 hour.

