#### **3.1.4 PRIMARY OBJECTIVES FOR PARTS C AND D (PHASE 2)**

- Evaluate preliminary efficacy (response rate, duration of response, disease control rate, landmark progression free survival rate, progression free survival, landmark overall survival, and overall survival) of JTX-2011 as monotherapy (Part C) and in combination with nivolumab (Part D) in subjects with specific advanced solid tumor malignancies;
- Part C: Confirm the safety and tolerability of JTX-2011 monotherapy in five (5) expansion groups, including 4 cohorts with stratification for ICOS expression: C01- head and neck squamous cell carcinoma [HNSCC]; C02 - non-small cell lung cancer [NSCLC]; C03 - advanced refractory solid tumors other than those eligible for C01, C02, C04, or C05; and C04- gastric cancer; and 1 cohort without stratification: C05- MSI-H or dMMR endometrial cancer;
- Part D: Confirm the safety and tolerability of JTX-2011 in combination with nivolumab therapy in six (6) indication specific expansion groups, including 5 with stratification for ICOS expression: D01-HNSCC; D02-NSCLC; D03-triple negative breast cancer (TNBC); D04- melanoma; D05- gastric cancer; and 1 cohort without stratification: D06- MSI-H or dMMR endometrial cancer;
- Confirm the maximum tolerated dose (MTD) and the recommended Phase 2 dose (RP2D) of JTX-2011 monotherapy (Part C) and JTX-2011 in combination with nivolumab (Part D) in subjects with advanced solid tumor malignancies.

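### Part C monotherapy adverse-event tables can include events that first arise after a PD-1 inhibitor is added, because the SAP sets no cut at the add-on

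*SAP*

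**What the plan says.** SAP 3.1.4 makes safety by cohort a primary objective: "Part C: Confirm the safety and tolerability of JTX-2011 monotherapy in five (5) expansion groups".

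Protocol 5.5 allows the regimen to change: "If a subject has progressed in Part C, nivolumab can be added to the" subject's treatment once progression is confirmed, if sponsor and investigator agree. Pembrolizumab may take nivolumab's place after Part G is complete. Protocol 7.3.1 lists both infusions at the same post-progression visit: "JTX-2011 Administration followed by observation for at least 1 hour" and "Nivolumab or pembrolizumab administration followed by observation for at least 1 hour".

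SAP 8.1.1 sets the TEAE window as "events that occur after the start of study drug(s) and on or before 28 days after final dose of study drug". The only thing it names as ending adverse-event collection early is cancer treatment given outside the protocol. SAP 7.2 tabulates Part C by tumor-type cohort unless stated otherwise. The SAP's adverse-event sections do not mention the post-progression add-on.

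**The concern.** A reader will take a Part C cohort column as the safety profile of JTX-2011 alone. If a subject progresses, adds a PD-1 inhibitor and then has a first serious event, the stated rules count that event in the same column. Protocol 1.6.2 itself expects that nivolumab's adverse events may become more frequent or more severe alongside JTX-2011, so the two periods cannot be assumed to be alike.

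At stake are the all-cause, serious, fatal, discontinuation and maximum-grade summaries, together with the treatment-emergent and maximum-grade laboratory summaries in SAP 9.9.2. Part C is also the natural comparison for Part D, and mixing regimens in Part C would blur that contrast.

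**Working it through.** The plan gives no figure on this point to reproduce, so the check is mainly textual.

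**1. Does the add-on extend the window?** Protocol 3.6 defines study drug to include the combinations, and SAP 6.1 names all four agents. The final dose of study drug can therefore be an add-on dose. Protocol 8.14.2 likewise times adverse-event recording from whichever agent was given last. The add-on is protocol treatment, so the early stop in SAP 8.1.1 does not apply.

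**2. Which column receives the event?** SAP 6.1 fixes the actual dose group by the first dose received. SAP 9.9.1 counts adverse events in the actual dose group, and SAP 7.2 makes the Part C columns tumor cohorts. A subject who adds a PD-1 inhibitor stays in the same cohort column.

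**3. Is there a cut elsewhere?**
- SAP 6.3 covers incorrect treatment, not a permitted addition.
- The new-therapy limit in SAP 9.1 applies to counting on-treatment deaths in the disposition summary.
- SAP 9.9 allows subsets to be shown but does not define this one.
- SAP 9.10.1 groups pharmacokinetic output by monotherapy or combination. The adverse-event tables have no such factor.

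**4. Size.** Protocol 5.5 and SAP 5 plan about 15 subjects per Part C cohort.
- One subject whose first event of a type follows the add-on: 1/15 = 6.7 points in the cohort column.
- With k add-on subjects in a cohort, the shift for one event type is at most k/15. It is 0 when k = 0. The documents give no value for k, so I put no likely figure on it.
- In a Part C total column: 1/75 = 1.3 points for the five cohorts in SAP 3.1.4 (5 × 15 = 75), or 1/120 = 0.8 points for the 120 planned subjects.

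Compared with a window cut at the add-on, the proportion of subjects with at least one event of a type can only rise. A rate per patient-year could move either way, because follow-up is added as well.

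**5. Nominal timing, q3w.** Protocol 7.2.11: "Response assessments will be performed within 10 days of C4D1, C7D1, C10D1, and every three cycles thereafter". Protocol 5.5: "Confirmatory scans may be performed no less than 4 weeks from the most recent radiographic assessment documenting disease progression".
- C4D1 = 1 + 3 × 21 = Day 64. The scan window opens 10 days earlier, on Day 54.
- Confirmatory scan at least 28 days later: 54 + 28 = Day 82.
- C5D1 = 1 + 4 × 21 = Day 85. With the 3-day visit window it can fall on Day 82.

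On schedule, the earliest add-on is therefore at Cycle 5, about Day 82, and Cycles 1 to 4 are monotherapy only. Cycles can be delayed (Protocol 6.7.1: "If the delay is more than 14 days, further course of treatment should be discussed with the Medical Monitor"). A delay can change which cycle carries the first add-on dose but cannot bring it before about Day 82. An unscheduled scan could, and SAP 9.11.1 provides for unscheduled assessments.

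**The case against.** The case on the other side has real content.

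- **By-cycle tables.** SAP 9.9.1 plans all-cause TEAEs, infusion reactions and immune-related events by cycle, with subjects dosed in that cycle as the denominator. On nominal q3w timing these show four clean monotherapy cycles. This stands, but the serious, fatal and discontinuation tables are not planned by cycle, and in later cycles subjects on either regimen are pooled.
- **Attribution by drug.** SAP 8.1.1 displays relatedness separately for each agent. This helps only the related-event tables, and JTX-2011 is given in both periods.
- **Exposure and listings.** SAP 9.8.1 summarizes exposure for JTX-2011 and for its combinations, and all adverse events are listed. A careful reader could place events against the add-on date by hand, but that is not a prespecified summary.
- **Intervals.** Protocol 9.4.8.1 foresees displays by time since the start of therapy, where appropriate. Three months is 3 × 30.4375 = 91.3 days, so on nominal timing the first such interval is nearly all monotherapy. Later ones can mix.
- **Table shells.** SAP 7.1 leaves layout to mock shells outside the sign-off. A period column could sit there, but it would not be a rule in the plan.

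A reader might go further and infer that Part C toxicity will be overstated, or that dose selection is affected. The documents do not support either. The add-on is discretionary and its count is not given. Dose-limiting toxicity is a Cycle 1 matter for the Phase 1 parts, and SAP 3.2.4.1 rests confirmation of the recommended dose on ICOS target engagement. Nor does the point carry over to RECIST response and progression-free survival: under SAP 8.3.3 and 8.3.5 best response is recorded only until documented progression, and progression-free survival ends there.

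**Conclusion.** The point holds for Part C safety tables. The SAP's own rules put combination-period events into columns intended to describe JTX-2011 monotherapy, and the planned displays offset this only in part. None of them splits the serious, fatal or discontinuation tables at the add-on.

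The firm figure is 6.7 points per affected subject in a 15-subject column. The total effect depends on how many subjects added a PD-1 inhibitor and then had a first event of a given type, and it may be zero. SAP 3.3.1 makes the safety analysis descriptive, so no test is affected, and mainly later-cycle events are involved. The change should be made because it protects the reading of a primary objective at little cost.

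**What to change.** **SAP 8.1.1.** For Part C subjects who add nivolumab or pembrolizumab, end the monotherapy-period TEAE window at the date of the first add-on infusion, or 28 days after the last monotherapy dose if that is earlier. Assign events by onset date. Assign events that start on the add-on day to the add-on period and flag them.

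**SAP 9.9.1.** Present the Part C TEAE tables for the monotherapy period. Summarize add-on-period events separately, with N equal to the subjects given at least one add-on dose. Keep the whole-study table, because late events may reflect earlier treatment and because it retains events in any gap between the periods. State whether immune-related event tables are planned for Part C: SAP 8.1.1 speaks of evaluating these events in the combination arms, while SAP 9.9.1 presents its tables for Phase 1 and Phase 2 parts alike.

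**SAP 9.9.2.** Apply the same period flag to the treatment-emergent and maximum-grade laboratory summaries, keeping the single baseline in SAP 7.3. No new laboratory reference value is needed.

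**Cost.** One derived variable from dosing dates already collected, short SAP wording and a few extra tables. One check is needed. Protocol 8.14.3 asks for a new record only when a pre-treatment event worsens, so confirm that on-treatment grade changes are dated. If they are not, an event that began on monotherapy and worsened after the add-on would carry its highest grade in the monotherapy table, and a footnote should say so.
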